## **11.0 Research Methods & Procedures**

Provide a detailed description of the methods and procedures that will be used to carry out the study. Include a summary of study visits and procedures (i.e., schedule of events table) in the space below or as an attachment.

Please make sure to include:

- Dosing of drugs and other details of study drug administration and study treatments
- A list and description of any experimental procedures
- A list and description all tests & procedures that would no be done if the subjects were not in the study
- An explanation how study participation differs from the standard of care
- Procedures being performed to monitor subjects for safety or to minimize risks

Eighteen low risk pregnant women with a singleton pregnancy will be recruited for this pilot project from Syracuse Community Health Center (50%), University OB/GYN Associates, and Upstate Community OB/GYN. All women will be enrolled during the 1st trimester (6 to 13-weeks' gestation) and without absolute contraindications to moderate intensity exercise during pregnancy as defined by American College of Sports Medicine (ACSM) and American College of Obstetricians and Gynecologists (ACOG). All participants will be cleared for exercise by their OB/GYN. The ACSM and ACOG guidelines include 150 min/wk of cardiovascular activity at a moderate intensity; 2-3 days/week of resistance training; and 2-3 days/wk of flexibility training. Clearance will come exclusively from the OB/GYN.

Women will be randomly assigned to either UA, EX or HOMEEX. Women randomized to EX will attend three exercise classes/week at the Institute for Human Performance (IHP) and given flexibility to attend classes between the hours of 7:30a-6p, Mon-Fri. Each session will consist of: 5-min flexibility warm-up and cool-down; 40 min of moderate intensity calculated as 40-59% Heart Rate Reserve (HRR) along with Rating of Perceived Exertion (RPE) between 13-14; and 20 minutes of resistance with an additional 30 minutes of unsupervised home aerobic activity per week. The women will be given their choice of aerobic equipment or walking either track/treadmill to achieve a total of 40 minutes of moderate intensity exercise.

Women assigned to HOMEEX will receive instructions for their home walking program including tips for walking indoors and outdoors, exercise handouts for warm-up/cool-down activities, demonstrations for resistance training activities and an exercise log. HOMEEX women will be contacted twice per week to discuss their progress, barriers/challenges faced, ask questions, and strategies to achieve the exercise guidelines. If women in either EX or HOMEEX are unable to achieve 30-40 minutes of continuous aerobic exercise at the start of the study, they will be given an individualized, progressive exercise program that breaks activity into smaller 10 minute sessions and/or increases rest between sessions to achieve the 150 minutes/week of moderate intensity activity.

Both exercise groups will receive exercise counseling during their first meeting in addition to materials on the benefits of exercise, a log to record additional activity completed each week, goal setting, making time for exercise/making exercise a habit and exercise behavioral strategies. The UA group will receive an exercise log to record any weekly activity in addition to a weekly phone call/text/email to remind the individual to download information from the Polar Ignite watch (Bethpage, NY) and a reminder to complete the weekly exercise log.

Each woman enrolled in the study will be given a Polar Ignite watch to wear for the study duration. This monitor will be programmed for moderate intensity HRR and will alarm if HR falls above/below during exercise for both exercise groups. In addition, the monitor will record all other activity within the HRR range and will be used to verify information obtained from activity and QOL questionnaires to reduce self-reported bias in all groups. For the control group, the watch will record activity by HR intensity level that can be quantified on a weekly basis.

Regardless of randomization, all women will report to the IHP between weeks 11-13 (late 1st trimester) for baseline testing and to review past medical history, medications and exercise history. Height will be measured to the nearest 0.25 inch using a stadiometer and converted to meters. BMI will be calculated using the self-reported pre-pregnancy weight. Gestational weight gain will be calculated from subtracting the pre-pregnancy weight from weight at the last obstetrics visit prior to delivery. All women will also perform a submaximal Balke-Ware

submaximal treadmill test to determine HRR for the two exercise groups and estimate VO2max using the Pollock equation which will be repeated at 3- and 6-months after birth to compare aerobic fitness levels.

All women will complete the following questionnaires at baseline (late 1st trimester), 25-26 weeks (late 2nd trimester), and 37-38 weeks (late 3rd trimester), and monthly through 6-months post-natal: MFI, SF-12 QOL; PSQLI; CES-D; EPDS; and the PPAQ. All questionnaires have been demonstrated to have good validity, reliability, and internal consistency and the CES-D and EPDS are similar to each other in regards to internal consistency and test-retest reliability.

Infants from mothers in all three groups will have their gross and fine motor, and cognitive development measured monthly (months 1-6) at home using the Bayley Scales of Motor Development, 4th edition. The Bayley 4 is a standardized, norm-referenced tool with subtest level scaled scores, domain level composite scores, percentile ranks, and developmental age equivalents. Infant height and weight will be measured monthly through 6-months of age.

Women assigned to EX will have all of their supervised pregnancy exercise sessions, questionnaires, and weight measured at the IHP. After delivery, women assigned to EX will resume their supervised IHP exercise program between 4-8 weeks (depending on delivery mode) when they are cleared for activity by their physician, complete exercise testing at 3- and 6-months and will have monthly home visits for infant testing through 6 months. HOMEEX and UC women will visit the IHP at baseline, 3 & 6-months post-delivery for exercise testing, questionnaires, and weight measurement. HOMEX and UC groups will receive home visits for: 2nd & 3rd trimester questionnaires and weight measurement and every month post-delivery for questionnaires, weight measurement and infant testing.

Statistical analysis used to determine feasibility of the exercise intervention will include general descriptive statistics to assess recruitment, eligibility, retention, follow-up and exercise adherence. In addition, we will conduct a survey and interview of subjects related to acceptability to participate in EX and HOMEEX and discuss barriers to regular exercise which will be analyzed using descriptive statistics and a phenomenological approach. To determine the feasibility of maternal and infant outcomes, Kruskal-Wallis and Friedman's ANOVA will be used to investigate between group and within group differences. Relationships between variables will be analyzed using Spearman correlation coefficient. Because this is a feasibility study, the results will be used as preliminary data to apply for future funding and also will provide variable quantitative and qualitative data for validating interventions that can increase adherence to exercise guidelines during pregnancy in women with different ethnic and socioeconomic backgrounds.

In order to monitor the safety of the participants, all exercise performed by the EX, HOMEEX, and UC groups will follow ACSM and ACOG guidelines for moderate-intensity cardiovascular and resistance exercise. In addition, all women will wear a Polar Ignite watch that will alarm if their HR exceeds moderate level intensity. All women in the EX will be supervised during their exercise sessions. Women in the HOMEEX group will be meet individually with either [name] or [name] to discuss safe exercise principles. They will be given written information on exercising in a moderate intensity range for both cardiovascular and resistance exercise. In addition, they will be contacted twice per week to discuss their program and any questions about exercise. Lastly, their HR data will be downloaded and analyzed to confirm that they are exercising in a moderate intensity rate. Women in the UC group will be told to continue participating in whatever activity they are currently engaged. They will be given an activity log to record their activity and we will download their HR data.

*11.1 Describe what data, including long-term follow-up, will be collected.*

*NOTE: For studies with multiple data collection points or long-term follow up, consider including a schedule or table in your response.*

Instruments being utilized in this study:

- The Bayley Scales of Infant Development, 4th edition
- Physical Activity diary
- Pregnancy Physical Activity Questionnaire
- Short-Form 12 (SF-12) Health survey
- Pittsburgh Sleep Quality Index
- Multidimensional Fatigue Inventory
- Edinburgh Post-Natal Depression Scale
- Center for Epidemiologic Studies Depression Scale

Activity	2020 September to December	2021 January to April	2021 May to August	2021 September to December	2022 January to April	2022 May to June
Recruitment (6 UC, 6 EX, 6 HOMEEX)	X					
Maternal Interventions	X	X	X	X	X	
Maternal Baseline Measurements	X	X				
Maternal Prenatal Measurements	X	X	X			
Maternal Post Natal Measurements			X	X	X	
Infant Measurements			X	X	X	X
Data Analysis				X	X	
Dissemination of results						X
First publication submission					X	
Target grant submission						X

*List, and upload, any instruments or measurement tools used to collect data (e.g. survey, scripts, questionnaire, interview guide, validated instrument, data collection form).*

*11.2 Describe any source records that will be used to collect data about subjects (e.g. school records, electronic medical records).*

n/a

*11.3 Describe whether individual subject results (such as results of investigational diagnostic tests, genetic tests, or incidental findings) will be shared with subjects or others (e.g., the subject's primary care physicians) and if so, describe how it will be shared.*

Participants will have access to the results of their testing immediately if requested but a summary of information will be provided to each participant at the end of their participation in the study.

Participants will independently choose if they wish to share any of their results with their primary care physician/OB/GYN

*11.4 Indicate whether or not generalized study results will be shared with subjects or others, and if so, describe how these will be shared.*

Overall (generalized) study results will be shared with participants at the completion of the study via an electronic and/or hard copy summary of results/findings.

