### **1.0 Objectives**

*1.1 Describe the purpose, specific aims, or objectives of this research. Specifically, explain why it is important to do the study.*

Historically, pregnant women were advised to refrain from exercise due to concerns of maternal and fetal risk such as preterm delivery, low infant birth rate and fetal stress. Despite current research that has demonstrated substantial benefits for maternal, fetal, and infant health, only 9-15% of pregnant women meet the current physical activity recommendations. In addition, pregnancy exercise research is confounded by a lack of randomized controlled trials (RCT) that include diversity in participant demographics, specifically inner city populations, and difficulty accurately quantifying weekly exercise volume. We propose a pilot RCT investigating two different approaches to exercise intervention across a spectrum of demographics that we believe will result in improved exercise adherence as well as in maternal and infant health outcomes.

*1.2 State the hypothesis to be tested, if applicable.*

*NOTE: A hypothesis is a specific, testable prediction about what you expect to happen in your study that corresponds with your above listed objectives.*

Specific Aim #1: To determine the feasibility of two types of exercise interventions (supervised & home exercise) in terms of design, implementation and adherence. Our working hypothesis is that both supervised and home exercise interventions will be implementable as designed in pregnant women as evidenced by recruitment, eligibility, retention, follow-up and exercise adherence from 1st trimester through 6-months post-natal at a 60% rate, but that adherence to the two types of exercise interventions will differ by demographic. A secondary exploratory hypothesis is that we will be able to successfully recruit and retain 50% of our pregnant women from the Syracuse Community Health Center (primarily women with lower resources).

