## **5.0 Data Management and Analysis**

*5.1 Describe the data analysis plan, including any statistical procedures. This section applies to both quantitative and qualitative analysis.*

Statistical analysis used to determine feasibility of the exercise intervention will include general descriptive statistics to assess recruitment, eligibility, retention, follow-up and exercise adherence. In addition, we will conduct a survey and interview of subjects related to acceptability to participate in EX and HOMEEX and discuss barriers to regular exercise which will be analyzed using descriptive statistics and a phenomenological approach. To determine the feasibility of maternal and infant outcomes, Kruskal-Wallis and Friedman's ANOVA will be used to investigate between group and within group differences. Relationships between variables will be analyzed using Spearman correlation coefficient. Because this is a feasibility study, the results will be used as preliminary data to apply for future funding and also will provide variable quantitative and qualitative data for validating interventions that can increase adherence to exercise guidelines during pregnancy in women with different ethnic and socioeconomic backgrounds.

*5.2 If applicable, provide a power analysis for the number of subjects to be included. If qualitative research, so state, and provide general justification for the total number of subjects proposed.*

*NOTE: This may not apply to certain types of studies, including chart/records reviews, survey studies, or observational studies. This question is asked to elicit whether the investigator has an adequate sample size to achieve the study objectives and justify a conclusion.*

This is a pilot project aimed to investigate feasibility of approach and appropriateness of maternal outcome measures. If the working hypotheses are supported, the next phase will be a large, randomized intervention study. Pilot data from this project can be utilized in the power analysis for the larger study.

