## **6.0 Local Number of Subjects**

6.1 *Indicate the total number of subjects who will be enrolled or records that will be reviewed through Upstate.*

No more than 18 total participants (six per group)

6.2 *If applicable, indicate your screen failure rate, i.e., how many subjects you expect to screen to reach your target sample.*

54 (anticipate that for every three women screened, one will participate in the study)

6.3 *Justify the feasibility of recruiting the proposed number of eligible subjects within the anticipated recruitment period. For example, how many potential subjects do you have access to? What percentage of those potential subjects do you need to recruit?*

The feasibility of recruitment is part of what is being investigated in this pilot project and findings from this project will inform the recruitment plan of the future large intervention study. The plan for the pilot is to recruit no more than 18 (six per group) low risk pregnant women with a singleton pregnancy from Syracuse Community Health Center (50%), University OB/GYN Associates, and Upstate Community OB/GYN. All women will be enrolled during the 1st trimester (6 to 13-weeks' gestation) and without absolute contraindications to moderate intensity exercise during pregnancy as defined by American College of Sports Medicine (ACSM) and American College of Obstetricians and Gynecologists (ACOG). All participants will be cleared for exercise by their OB/GYN.

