While we will not be analyzing the data (e.g. results of depression or other questionnaires) during the study to avoid compromising interactions (e.g. bias) with participants, study personnel will be speaking to participants in the HOMEEX and EX groups multiple times per week. Participants will be asked about their next OB/GYN appointment and if anything about their health status has changed (this helps to also insure that each participant is maintaining an active relationship with her OB provider). The physician approval form that provides a participant with clearance to participate in the study will include a statement that asks the physician to inform study personnel immediately if the participant develops any contraindication, relative or absolute, to participation in an exercise program (e.g. fetal growth restriction or gestational hypertensive disorder). Gestational diabetes mellitus (GDM) will be handled per individual participant's OB/GYN recommendations. If a participant develops an absolute contraindication to participation in the study, they will be removed from the study. If a participant experiences an adverse event, a new clearance must be provided by OB/GYN for the participant to return to the study. In the case of an emergency, participants will be advised to seek care at Upstate Community Hospital. If a participant needs NICU care, they will be advised to seek care at Crouse or St. Joseph's hospital.

Only full term infants (birth at 37+ weeks gestation) will go on to participate in the neonatal portion of the study. Infants participating in this portion of the study will undergo monthly height, weight, motor and cognitive assessments that pose minimal to no risk to the infant. In the

event, that an assessment uncovers unexpected information (e.g. loss of weight, significantly delayed motor development), participants will be advised to contact their pediatrician.

Participants will regularly be asked how they are feeling. If a participant expresses that she is feeling blue or is having depressive thoughts, study personnel will recommend that she contact her health provider. We will follow up each week to check the status of these symptoms and to make sure they have spoken with their health provider. Participants in the control group are also being contacted weekly, so relationships are being established, and the same process for experiencing undesirable thoughts or feelings would apply.

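### No age- and sex-standardised scale is named for infant weight and height; on the measurements as taken, the within-arm Friedman test would only register that infants grow

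*Combined protocol and SAP*

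**What the plan says.** On the data, section 11.0 states "Infant height and weight will be measured monthly through 6-months of age". Section 19.4 mentions the same monthly measurements. Neither place names a growth reference, a z-score or percentile, an adjustment for sex or exact age, or a visit window.

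Just before this, section 11.0 describes the Bayley 4 as norm-referenced and lists its scaled scores, composite scores, "percentile ranks, and developmental age equivalents". Nothing comparable is given for weight and height, and the plan does not say which Bayley score will be analysed.

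On the analysis, section 11.0 states "To determine the feasibility of maternal and infant outcomes, Kruskal-Wallis and Friedman's ANOVA will be used to investigate between group and within group differences", and section 5.1 says the same. No significance level is given.

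On numbers, section 6.1 caps enrolment at 18, six per arm. Specific Aim 1 in section 1.2 sets a feasibility target for "recruitment, eligibility, retention, follow-up and exercise adherence from 1st trimester through 6-months post-natal at a 60% rate". Section 19.4 adds: "Only full term infants (birth at 37+ weeks gestation) will go on to participate in the neonatal portion of the study".

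**The concern.** Friedman's test uses only the rank order of each infant's own values over time. Weight and height normally rise from one month to the next in the first half-year, so on measured values each infant's ranks run from 1 to 6 whatever the arm and however fast the gain. The test then answers a question nobody is asking.

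What is at stake is how the result will be read. The plan uses these tests to judge whether the infant measures are workable, and section 5.1 says the findings will support later funding applications. A significant within-arm change in weight could be taken as a sign that the measure responds to the programme. Slowed but positive growth in one arm would give the same within-arm result.

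The between-arm comparison is not empty in this way. On measured values, however, it carries variation from infant sex and from exact age at the visit, in arms of six or fewer.

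**Working it through.** The plan gives no power, significance level or effect size for infant outcomes, so there is no figure of its own to reproduce.

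**Inputs**
- Visits: k = 6. This is assumed from monthly measurement to month 6 in section 11.0.
- Infants per arm: n = 6 at most (section 6.1). At the 60% target in section 1.2, 0.60 × 6 = 3.6, so 3 or 4.
- Significance level: 0.05, assumed.

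**Step 1: Friedman when every infant gains at every visit.** The statistic is Q = 12/[nk(k+1)] × ΣRⱼ² − 3n(k+1), where Rⱼ is the rank sum at visit j. With perfect ordering Rⱼ = nj, so ΣRⱼ² = n²k(k+1)(2k+1)/6. Then Q = 2n(2k+1) − 3n(k+1) = n(k−1), which is 5n for k = 6. The reference distribution is chi-square with 5 df.

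| n | Q | p (chi-square) |
|---|---|---|
| 6 | 30 | 0.000015 |
| 4 | 20 | 0.0012 |
| 3 | 15 | 0.010 |
| 2 | 10 | 0.075 |

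The chi-square p-values are conservative here. The exact probability that all n rankings agree is (1/720)^(n−1), which is 0.0014 even for two infants. The growth rate does not enter the formula.

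**Step 2: simulation of a slower arm.** Two arms grow normally and one gains a fraction f of normal. The documents give no growth figures, so all of the following are assumptions, in between-infant SD units: normal gain 0.5 to 1.0 SD per month, visit noise 0.2 SD, slope coefficient of variation 20%. There were 800 runs per setting. Entries are rejection rates across the range of assumed gains.

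| n per arm | f | Friedman, slower arm | Kruskal-Wallis, month-6 value | Kruskal-Wallis, month 1 to 6 gain |
|---|---|---|---|---|
| 6 | 0.75 | 1.00 | 0.10–0.26 | 0.42–0.52 |
| 6 | 0.50 | 1.00 | 0.39–0.86 | 0.98–1.00 |
| 6 | 0.25 | 0.97–1.00 | 0.73–1.00 | 1.00 |
| 4 | 0.75 | 1.00 | 0.08–0.15 | 0.23–0.31 |
| 4 | 0.50 | 1.00 | 0.24–0.54 | 0.82–0.92 |

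Friedman rejects in 1.00 of runs in the normally growing arms too. At f = 0 (no growth at all) it rejects in only 0.04–0.05 of runs with n = 6.

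**Step 3: what a standardised scale would do.** No z-score can be computed from the documents, because they contain no growth reference. Two rows of the simulation act as stand-ins. The f = 0 case has no trend over time, as a flat z-score would, and there Friedman rejects at about the nominal rate. The gain column approximates an analysis of change. Both assume independent noise between visits, and neither models sex.

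**Step 4: visit age.** No visit window is stated. If one infant were seen 7 days early and another 7 days late (assumed), the 14-day gap at 0.5 to 1.0 SD per month would be worth 14/30 × 0.5 = 0.23 to 14/30 × 1.0 = 0.47 SD from age alone.

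**The case against.** The strongest reply is that the plan does not say measured values will be analysed. That is correct. A reader might infer it from the wording of section 11.0, but the documents are silent on the scale, so everything in Step 1 is conditional.

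A reader might also infer that slowed growth would escape the whole plan. It would not. The sentence that names Friedman also names Kruskal-Wallis between randomised arms, all restricted to term infants. Step 2 shows that this test picks up severe slowing reasonably often on raw month-6 values. Growth arrest would change the Friedman result as well. Part of the low power for modest slowing is simply pilot size: even on gain it is only 0.42–0.52 with six per arm.

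The documents do not make infant growth a main safety measure either. Section 17 names no safety endpoint, and Aim 2 and section 2.1 concern maternal measures. The example in section 19.4, "loss of weight, significantly delayed motor development", describes when a family is advised to contact the pediatrician. It is a separate safeguard for the individual infant and says nothing about the analysis scale.

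A worry that Bayley raw scores or age equivalents will be analysed would be speculation, since norm-referenced scores are listed first and no choice is stated.

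Finally, an identical significant Friedman result in the control arm would itself caution against crediting the programme. That limits the risk of misreading. It does not make the within-arm test informative.

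**Conclusion.** The point holds as a conditional one. The plan names a within-arm test for infant outcomes and no standardised scale for weight and height. On values as taken, that test is significant in any arm of three or more infants who gain at every visit, and it cannot separate normal from slowed but positive growth. This part is algebra and needs only k = 6, consistent gain and a 0.05 level.

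The between-arm test remains able to show a slower arm, with low power for modest slowing at 4 to 6 infants per arm. Those power figures depend on the assumed growth rates and are indicative only.

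Infant outcomes do not drive the pilot's stated endpoint, and no decision rule rests on an infant p-value. The change should nevertheless be made before analysis, because it replaces an uninformative test with a usable one at little cost.

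**What to change.** Add to sections 5.1 and 11.0 a statement to this effect:

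- Infant weight and height (taken as length at this age) are converted at each visit to age- and sex-specific z-scores from a named published growth standard, using exact age in days.
- These z-scores, or their change from the first visit, are the values analysed within and between arms. Between-arm differences are given with estimates and intervals.
- Kilograms and centimetres are reported descriptively only.
- For the Bayley, the scaled or composite scores already described in section 11.0 are the values analysed.

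Any within-arm drift in z-score should be read against the control arm, since a small local sample need not follow the reference exactly.

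The cost is a few sentences and three data items: infant sex, birth date and visit date. The documents do not list these as collected, and section 11.2 names no source records, so they should be added to the data collection form. No extra visit is needed, and no change to any referral rule is proposed. Standardisation will not overcome the small arms; it makes the comparison interpretable and removes avoidable noise.
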